5.3.8. Patient Reported Outcome Measurement Information System-Sleep Disturbance (PROMIS-SD)

5.3.8.1. Definition

A secondary efficacy endpoint is the change from baseline to Weeks 12 and 24 in the PROMIS-SD. The PROMIS-SD Short Form subscale consists of a static 8-item questionnaire. Using a recall period of the past 7 days, it assesses the concepts of sleep initiation (2 items), quality of sleep (3 items), early morning feelings (2 items) and worrying about sleep (1 item).

Each question has five response options ranging in value from one to five. To find the total raw score for a short form with all questions answered, sum the values of the response to each question. For the 8-item form, the lowest possible raw score is 8; the highest possible raw score is 40. Lower scores indicate less sleep disturbance. Note that the "direction" of the responses is not the same for all questions, i.e., sometimes a response of "not at all" indicates more sleep disturbance and sometimes a response of "not at all" indicates less sleep disturbance.

- “My sleep quality was” ranges from 5=very poor to 1=very good
“My sleep was refreshing” ranges from 5=not at all to 1=very much
“I had a problem with my sleep” ranges from 1=not at all to 5=very much
“I had difficulty falling asleep” ranges from 1=not at all to 5=very much
“My sleep was restless” ranges from 1=not at all to 5=very much
“I tried hard to get to sleep” ranges from 1=not at all to 5=very much
“I worried about not being able to fall asleep” ranges from 1=not at all to 5=very much
“I was satisfied with my sleep” ranges from 5=not at all to 1=very much

A score can be approximated if a participant skips a question. However, for the 8-item form, at least 4 items must have been answered in order to calculate a score. After confirming that enough responses were provided, sum the response scores from the items that were answered. Multiply this sum by the total number of items in the short form. Finally, divide by the number of items that were answered. For example, if a respondent answered 5 of 8 questions and answered all items with the second lowest response option (2), you would sum all responses (10), multiply by the number of items in the short form (8) and divide by the number of items that were answered (5). Here $(10 \times 8) / 5 = 16$. If the result is a fraction, round up to the nearest whole number.

The formula is:

$(\text{Raw sum} \times \text{number of items on the short form}) / \text{Number of items that were actually answered}$

This is a pro-rated raw score.

The raw score (i.e., the total raw score or pro-rated raw score) can be converted into a T-score for each participant based on the table in Attachment 2. The T-score rescales the raw score into a standardized score with a mean of 50 and an SD of 10.

The change in the PROMIS-SD score from baseline to each time point in the double-blind phase will be calculated, for both the raw score and the T-score.

5.3.8.2. Analysis Methods

Descriptive statistics of the actual values on Baseline, Week 2, Week 6, Week 12, Week 18, and Week 24 and the change from baseline to each postbaseline time point will be presented for PROMIS-SD raw score and the T-score by treatment group.

The change from baseline to each postbaseline time point in the PROMIS-SD raw score and the T-score will be analyzed using the same MMRM as described in Section 5.3.1.2 for MADRS total score, with the covariate “baseline MADRS total score” changed to “baseline PROMIS-SD raw score” or “baseline PROMIS-SD T-score”, respectively.

Frequency distributions of the PROMIS-SD individual items will be provided at each assessment time point by treatment group.

5.3.9. Patient Reported Outcome Measurement Information System- Sleep Related Impairment (PROMIS-SRI)

5.3.9.1. Definition

A secondary efficacy endpoint is the change from baseline to Weeks 12 and 24 in the PROMIS-SRI. The PROMIS-SRI Short Form subscale consists of a static 8 item questionnaire. The PROMIS adult Sleep-Related Impairment item bank focuses on self-reported perceptions of alertness, sleepiness, and tiredness during usual waking hours, and the perceived functional impairments during wakefulness associated with sleep problems or impaired alertness. Though Sleep-Related Impairment does not directly assess cognitive, affective, or performance impairment, it does measure waking alertness, sleepiness, and function within the context of overall sleep-wake function. The Sleep-Related Impairment short form is universal rather than disease-specific. It assesses sleep-related impairment over the past 7 days.

Each question has five response options ranging in value from one to five. To find the total raw score for a short form with all questions answered, sum the values of the response to each question. For the 8-item form, the lowest possible raw score is 8; the highest possible raw score is 40. Lower scores indicate less sleep related impairment. Note that the “direction” of the responses is not the same for all questions, i.e., sometimes a response of “not at all” indicates more sleep related impairment and sometimes a response of “not at all” indicates less sleep related impairment.

“I had a hard time getting things done because I was sleepy” ranges from 1=not at all to 5=very much

“I felt alert when I woke up” ranges from 5=not at all to 1=very much

“I felt tired” ranges from 1=not at all to 5=very much

“I had problems during the day because of poor sleep” ranges from 1=not at all to 5=very much

“I had a hard time concentrating because of poor sleep” ranges from 1=not at all to 5=very much

“I felt irritable because of poor sleep” ranges from 1=not at all to 5=very much

“I was sleepy during the daytime” ranges from 1=not at all to 5=very much

“I had trouble staying awake during the day” ranges from 1=not at all to 5=very much

A score can be approximated if a participant skips a question. However, for the 8-item form, at least 4 items must have been answered in order to calculate a score. After confirming that enough responses were provided, sum the response scores from the items that were answered. Multiply this sum by the total number of items in the short form. Finally, divide by the number of items that were answered. For example, if a respondent answered 5 of 8 questions and answered all items with the second lowest response option (2), you would sum all responses (10), multiply by the number of items in the short form (8) and divide by the number of items that were answered (5). Here $(10 \times 8) / 5 = 16$. If the result is a fraction, round up to the nearest whole number.

The formula is:

(Raw sum x number of items on the short form) / Number of items that were actually answered

This is a pro-rated raw score.

The total raw score or pro-rated score can be converted into a T-score for each participant based on the table in Attachment 3. The T-score rescales the raw score into a standardized score with a mean of 50 and an SD of 10.

The change in the PROMIS-SRI score from baseline to each time point in the double-blind phase will be calculated, for both the raw score and the T-score.

5.3.9.2. Analysis Methods

Descriptive statistics of the actual values on Baseline, Week 2, Week 6, Week 12, Week 18, and Week 24 and the change from baseline to each postbaseline time point will be presented for PROMIS-SRI raw score and the T-score by treatment group.

The change from baseline to each postbaseline time point in the PROMIS-SRI raw score and the T-score will be analyzed using the same MMRM as described in Section 5.3.1.2 for MADRS total score, with the covariate “baseline MADRS total score” changed to “baseline PROMIS-SRI raw score” or “baseline PROMIS-SRI T-score”, respectively.

Frequency distributions of the PROMIS-SRI individual items will be provided at each assessment time point by treatment group.

5.3.10. Symptoms of Major Depressive Disorder Scale (SMDDS)

5.3.10.1. Definition

A secondary efficacy endpoint is the change from baseline to Weeks 12 and 24 in the SMDDS. The SMDDS assesses patient-reported symptoms associated with MDD. The target population includes adults (aged 18 and older) with a clinical diagnosis of MDD who are being treated in an ambulatory setting. The SMDDS has been developed in a patient sample including both males and females, varying levels of age, race, education, marital status, and severity. This 16-item instrument has a 7-day recall period, and subjects respond to each question using a rating scale between 0 (“Not at all” or “Never”) to 4 (“Extremely” or “Always”). Before summing the items to create a total score, item 11 (“how often did you have a poor appetite”) and item 12 (“how often did you over eat”) are combined into a single score by selecting the highest severity on either item. The total score is then created by summing the responses on the 15 items. The total score ranges from 0 to 60 with a higher score indicating more severe depressive symptomatology.

5.3.10.2. Analysis Methods

Descriptive statistics of the actual values on Baseline, Week 2, Week 4, Week 6, Week 12, Week 18, and Week 24 and the change from baseline to each postbaseline time point will be presented for SMDDS total score by treatment group.

The change from baseline in SMDDS total score will be analyzed using the same MMRM as described in Section 5.3.1.2 for MADRS total score, with the continuous covariate “baseline MADRS total score” changed to “baseline SMDDS total score”.

Frequency distributions of the SMDDS individual items will be provided at each assessment time point by treatment group.

5.3.11. Symbol Digit Modalities Test (SDMT)

5.3.11.1. Definition

A secondary efficacy endpoint is the change from baseline to Weeks 6, 12, and 24 in the SDMT. The SDMT is a widely used, paper-and-pencil assessment of complex scanning and visual tracking, requiring elements of attention, visuoperceptual processing, working memory, and cognitive/psychomotor speed. The test is viewed as a robust screening test for adult neuropsychological impairment and is sensitive to impairments in cognitive function associated with MDD. The SDMT measures the time to pair abstract symbols with specific numbers. The test includes a coding key consisting of 9 abstract symbols, each paired with a number ranging from 1 to 9. Following the key, the subject is presented with randomly ordered symbols and is required to write the number corresponding to each symbol as fast as possible. The number of correct substitutions within 90 seconds is recorded.

5.3.11.2. Analysis Methods

Descriptive statistics of the actual values on Baseline, Week 6, Week 12, and Week 24 and the change from baseline to each postbaseline time point will be presented for SDMT score by treatment group.

The change from baseline in SDMT score will be analyzed using the same MMRM as described in Section 5.3.1.2 for MADRS total score, with the continuous covariate “baseline MADRS total score” changed to “baseline SDMT score”.

5.3.12. Trail Making Test – Part B (TMT–Part B)

5.3.12.1. Definition

A secondary efficacy endpoint is the change from baseline to Weeks 6, 12, and 24 in the TMT-Part B. The TMT-Part B measures divided attention and executive function (tracking and sequencing). The subject is instructed to draw a line to connect a set of 25 consecutively numbered and lettered circles, alternating sequentially between numbers and letters (i.e., 1 A 2 B). The subject is instructed to work as quickly as possible while still maintaining accuracy. The TMT-Part B is sensitive to cognitive decline associated with MDD.

5.3.12.2. Analysis Methods

Descriptive statistics of the actual values on Baseline, Week 6, Week 12, and Week 24 and the change from baseline to each postbaseline time point will be presented for TMT-Part B score by treatment group.

The change from baseline in TMT-Part B score will be analyzed using the same MMRM as described in Section 5.3.1.2 for MADRS total score, with the continuous covariate “baseline MADRS total score” changed to “baseline TMT-Part B score”.

5.3.13. Hopkins Verbal Learning Test-Revised (HVLTR)

5.3.13.1. Definition

A secondary efficacy endpoint is the change from baseline to Weeks 6, 12, and 24 in the HVLTR. The HVLTR, a measure of verbal learning and memory, is a 12-item word list recall test. Administration includes 3 learning trials, a delayed recall (20-minute) trial, and a 24-word recognition list (including 12 target and 12 foil words). The test administrator reads instructions and word lists aloud, and records words recalled/recognized by the subject. Scores include learning, delayed recall, and recognition. The HVLTR is a well-validated and widely used measure of verbal episodic memory.

5.3.13.2. Analysis Methods

Descriptive statistics of the actual values on Baseline, Week 6, Week 12, and Week 24 and the change from baseline to each postbaseline time point will be presented by treatment group for the following: total recall (sum of total correct responses for Trials 1, 2, and 3), delayed recall (number of correct responses for Trial 4), total number of true-positive errors, and recognition discrimination index (total number of true positives minus total number of false positives).

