
 
To assess the efficacy of JNJ-42847922 compared to quetiapine XR as adjunctive therapy for MDD in the improvement of global depressive symptom severity.
 
	
 
Change from baseline to Weeks 12 and 24 in the Clinical Global Impression—Severity (CGI-S) score.
 

 
To characterize subject perceptions of global MDD severity.
 
	
 
Change from baseline to Weeks 12 and 24 in the Patient Global Impression-Severity (PGI-S) score.
 

 
To assess the effect of JNJ-42847922 compared to quetiapine XR as adjunctive therapy for MDD on the subject's assessment of quality of life.
 
	
 
Change from baseline to Weeks 12 and 24 in Quality of Life in Depression Scale (QLDS).
 

 
To assess the effect of JNJ-42847922 compared to quetiapine XR as adjunctive therapy for MDD on the subject's assessment of sleep impairment and daytime problems due to lack of sleep.
 
	
 
Change from baseline to Weeks 12 and 24 in Patient Reported Outcomes Measurement Information System-Sleep Disturbance (PROMIS-SD Short Form 8a).
 
Change from baseline to Weeks 12 and 24 in Patient Reported Outcomes Measurement Information System-Sleep-Related Impairment (PROMIS-SRI Short Form 8a).
 

 
To assess the effect of JNJ-42847922 compared to quetiapine XR as adjunctive therapy for MDD on the subject's assessment of reduction of depressive symptoms.
 
	
 
Change from baseline to Weeks 12 and 24 in Symptoms of Major Depressive Disorder Scale (SMDDs)
 

 
To assess the effect of JNJ-42847922 compared to quetiapine XR as adjunctive therapy for MDD on cognitive function.
 
	
 
Change from baseline to Weeks 6, 12, and 24 in Symbol Digit Modalities Test (SDMT).
 
Change from baseline to Weeks 6, 12, and 24 in Trail Making Test - Part B (TMT-Part B).
 
Change from baseline to Weeks 6, 12, and 24 in Hopkins Verbal Learning Test-Revised (HVLt-R).
 

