
 To assess the effect of JNJ-42847922 compared to quetiapine XR as adjunctive therapy for MDD on the subject's assessment of sleep impairment and daytime problems due to lack of sleep. 	
 Change from baseline to Weeks 12 and 24 in Patient Reported Outcomes Measurement Information System-Sleep Disturbance (PROMIS-SD Short Form 8a). Change from baseline to Weeks 12 and 24 in Patient Reported Outcomes Measurement Information System-Sleep-Related Impairment (PROMIS-SRI Short Form 8a).

 To assess the effect of JNJ-42847922 compared to quetiapine XR as adjunctive therapy for MDD on the subject's assessment of reduction of depressive symptoms. 	
 Change from baseline to Weeks 12 and 24 in Symptoms of Major Depressive Disorder Scale (SMDDSD)

 To assess the effect of JNJ-42847922 compared to quetiapine XR as adjunctive therapy for MDD on cognitive function. 	
 Change from baseline to Weeks 6, 12, and 24 in Symbol Digit Modalities Test (SDMT). Change from baseline to Weeks 6, 12, and 24 in Trail Making Test - Part B (TMT-Part B). Change from baseline to Weeks 6, 12, and 24 in Hopkins Verbal Learning Test-Revised (HVLT-R).

CCI
	
 Change from baseline to Weeks 6 and 24 in salivary cortisol levels as measured at home upon awakening and at home during the evening.

Objectives	Endpoints

 To assess the safety and tolerability of JNJ-42847922 compared with quetiapine XR as adjunctive treatment in subjects with MDD. 	
 Safety assessments including: 
 Adverse events (AEs). Proportion of all serious adverse events (SAEs) and events of special interest (e.g., parasomnias). Vital signs, physical examinations, electrocardiogram (ECG), and laboratory parameters. Sexual functioning using the Arizona Sexual Experiences Scale (ASEX). Extrapyramidal symptoms assessed by the Extrapyramidal Symptom Rating Scale-Abbreviated (ESRS-A). Suicidality assessed using the Columbia Suicide Severity Rating Scale (C-SSRS). Potential withdrawal effects assessed by the Physician Withdrawal Checklist (PWC).
Exploratory	

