5.1. Analysis Specifications

5.1.1. Level of Significance

The primary efficacy endpoint will be evaluated at a two-sided significance level of 0.20. For all other efficacy endpoints, no multiplicity adjustment will be done and point estimates and confidence intervals will be presented.

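### HVLT-R is a secondary endpoint under a comparative objective, but SAP 5.3.13.2 pre-specifies no between-arm estimate or interval for it, unlike SDMT and TMT-Part B

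*SAP*

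**What the plan says.** The SAP states the cognitive objective as a comparison: "To assess the effect of JNJ-42847922 compared to quetiapine XR as adjunctive therapy for MDD on cognitive function" (SAP 1.1; Protocol 2.1 has the same objective). Three tests serve it: SDMT, TMT-Part B and HVLT-R. SAP 5.3.13.1 gives the last its status: "A secondary efficacy endpoint is the change from baseline to Weeks 6, 12, and 24 in the HVLTR". SAP Table 4 also lists it as secondary.

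For efficacy endpoints other than the primary, SAP 5.1.1 states: "For all other efficacy endpoints, no multiplicity adjustment will be done and point estimates and confidence intervals will be presented". Protocol 11.3 leaves the secondary analyses to the SAP and itself promises nominal p-values.

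For SDMT, SAP 5.3.11.2 gives descriptive tables and then a model: "The change from baseline in SDMT score will be analyzed using the same MMRM as described in Section 5.3.1.2 for MADRS total score". SAP 5.3.12.2 does the same for TMT-Part B. The model in SAP 5.3.1.2 adjusts for the baseline score and insomnia status and yields an 80% interval for the difference in LS means at each visit.

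For HVLT-R, SAP 5.3.13.2 stops at the descriptive tables. Statistics of actual values and changes from baseline "will be presented by treatment group for the following: total recall", followed by delayed recall, "total number of true-positive errors" and the recognition discrimination index.

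**The concern.** The protocol describes the trial's purpose as finding features that differentiate the two drugs. HVLT-R is the verbal-memory test among the three cognitive measures, and it is the only one of them with no planned contrast. Two exploratory endpoints, the sleep diary and MADRS-WOSI, receive the MMRM, so this secondary endpoint is handled less fully than they are, and the SAP gives no reason.

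At stake is pre-specification. Four HVLT-R scores are listed and none is designated as the endpoint. With no stated contrast, covariates or lead score, any between-arm statement about verbal memory would involve choices made after the data are seen. The descriptive tables also rest on whoever is still being assessed at each visit, and the planning assumptions expect persistence on treatment to differ between arms.

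A smaller matter sits in the same sentence. A true positive on a recognition list is a correct response, so a count of true-positive errors cannot be programmed as written.

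**Working it through.** **1. Planned analyses side by side**

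| Test | Status | Descriptive tables | Model and interval |
|---|---|---|---|
| SDMT (5.3.11.2) | Secondary | Yes | MMRM, 80% CI |
| TMT-Part B (5.3.12.2) | Secondary | Yes | MMRM, 80% CI |
| HVLT-R (5.3.13.2) | Secondary | Yes | None |

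No other SAP section supplies an HVLT-R contrast. Where the SAP spells out descriptive statistics (4.1, 4.4, 6.3), it means N, mean, SD, median and range. The descriptive tables therefore do not meet 5.1.1 by another route.

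**2. Planning inputs** (Protocol 11.2, SAP 1.4): 50 subjects per arm, 50% discontinuation on quetiapine XR, hazard ratio 0.415, 1-sided 0.10, about 92% power.

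First, the plan's own figure:
- Retention on JNJ-42847922 under proportional hazards: 0.5^0.415 = 0.75, so 25% discontinue.
- Expected events: 50 × 0.50 + 50 × 0.25 = 37.5.
- Schoenfeld power: Φ(√37.5 × |ln 0.415| / 2 − 1.2816) = Φ(1.411) = 0.921. The stated 92% is reproduced.

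**3. Subjects behind the Week 24 HVLT-R means**
- Quetiapine XR: 50 × 0.50 = 25.
- JNJ-42847922: 50 × 0.75 = 37.5, so 37 or 38.

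These are approximate. The HVLT-R Week 24 window in SAP Table 1 opens at Day 127, so an assessment before Day 168 can count. The protocol's Time and Events Schedule places HVLT-R at baseline and Weeks 6, 12 and 24 and not at the end-of-study visit, so early leavers have no scheduled exit score.

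**4. Is an interval feasible at this size?** Half-width of an unadjusted 80% CI, in SD units of the outcome, is 1.2816 × √(1/n₁ + 1/n₂).
- 50 and 50: 1.2816 × 0.200 = 0.26 SD.
- 25 and 37.5: 1.2816 × 0.258 = 0.33 SD.

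So it is feasible.

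**5. What baseline adjustment adds over raw change.** Take one visit, subjects with complete data, and equal variances σ² at baseline and follow-up with correlation ρ. The per-subject variance is 2σ²(1 − ρ) for change and σ²(1 − ρ²) after adjustment. The ratio is (1 + ρ)/2, and interval width scales with its square root. The documents give no value of ρ, so a range is assumed.

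| ρ (assumed) | Variance ratio | Variance cut | Width cut |
|---|---|---|---|
| 0.5 | 0.75 | 25% | 13% |
| 0.6 | 0.80 | 20% | 11% |
| 0.7 | 0.85 | 15% | 8% |

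**The case against.** The best defence is that the arms can still be compared. SAP 5.3.13.2 plans change from baseline by arm, which is already a simple allowance for baseline. With N, mean and SD of change, anyone can compute an unadjusted difference and its 80% interval. That is correct. A reader might infer that verbal memory has no between-arm answer at all, and the documents do not support that. What is missing is a pre-specified, model-based estimate.

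A reader might also infer that the MMRM would remove the selection caused by dropout. It would not do so in general. It uses the earlier visits of subjects who later leave, but it corrects the comparison only if missingness is at random, and a subject who stops before any post-baseline HVLT-R contributes nothing under either approach. SDMT and TMT-Part B share the same visits and the same attrition.

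Nor is HVLT-R the only departure from 5.1.1. CGI-S and PGI-S have a rank ANCOVA with no interval stated (5.3.5.2, 5.3.6.2), and MADRS by insomnia subgroup is descriptive only (5.3.1.2). It is fair to say that 5.1.1 is a general sentence under a heading about significance level and is worded more broadly than several sections beneath it. That points to tidying those sections as well. It does not explain why one of three tests under one objective is treated differently.

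The precision gain is modest and rests on an assumed correlation. Modelling three scores at three visits produces nine unadjusted contrasts, so a lead score is needed. The point about "total number of true-positive errors" is editorial: the same sentence builds the discrimination index from true and false positives, so the components can be identified.

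**Conclusion.** The inconsistency is real and limited. One of the three secondary cognitive endpoints has no pre-specified between-arm estimate, interval or adjusted model, contrary to SAP 5.1.1 and to the treatment of SDMT and TMT-Part B. The change should be made, but the primary analysis and its 92% power do not depend on it.

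A hand-derived comparison would be unadjusted, would rest on about 25 versus 37 or 38 subjects at Week 24, and would have an interval wider than the baseline-adjusted one. Moving to the adjusted analysis would narrow that interval by about 8% to 13%. The counts assume 50% discontinuation on quetiapine XR, proportional hazards at 0.415, and Week 24 scores only from those who stay on drug. The width figures assume ρ between 0.5 and 0.7 and do not measure any bias from dropout.

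**What to change.** In SAP 5.3.13.2:

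- Add that change from baseline in total recall, delayed recall and the recognition discrimination index will each be analysed with the MMRM of Section 5.3.1.2, replacing the MADRS covariate with the matching baseline HVLT-R score, and reporting the LS mean difference and 80% CI at Weeks 6, 12 and 24.
- Name one score, for example total recall, as the lead HVLT-R measure, with the others supportive.
- Note that this analysis addresses dropout only under missing-at-random.
- Replace "total number of true-positive errors" with the recognition count intended, either true positives or false-positive errors.

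If descriptive reporting alone was intended, SAP 5.1.1 should name HVLT-R as an exception and give the reason.

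The cost is one SAP paragraph and a few extra model runs reusing the specification already in place for SDMT and TMT-Part B. No new data are needed.
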